In Rwanda, a Sub-Saharan country the size of Jutland and with around 12 million citizens, the total number of medical doctors specialized in mental health is 13 in the year of 2019. So far, no treatment guidelines on mental health disorders including BD exist in Rwanda. To date, there is no data on incidence, prevalence or prognosis for BD in Rwanda.

Rwanda's health care system is organized along the principles of the WHO on primary health care(15,16). Health Centres are the first point of contact for patients. These centres also coordinate all outreach and prevention activities held at the community level, carried out by Community Health Workers (CHWs). The next level of care is the 41 District Hospitals, which has a mental health department staffed by a permanent team of psychiatric nurses and a psychologist. At the top of the mental health care system there are two national referral hospitals. The Neuropsychiatric Hospital of Ndera and the Mental Health Department of Kigali Teaching Hospital (CHUK), where only Ndera Hospital provides inpatient care. Statistics from the 2017 annual report at Ndera Hospital and CHUK shows that the annual numbers of outpatient visits with a diagnosis of BD were 1710 and 700, respectively. No data on BD is available on district or community level.

The efficacy of psychoeducation as an add-on treatment to pharmacotherapy is well documented in the treatment of symptoms and in relapse prevention initiatives with respect to BD in western countries(17). Psychoeducation is believed to empower the patient to take an active role in the therapeutic process, thereby potentially reducing stigma, guilt, and

helplessness, as well as improving medical adherence and to engage caregivers(18). Yet, no studies on psychosocial interventions for BD have been conducted in a low-income country(19).

In September 2014, the outpatient clinic of the Mental Health Department of Kigali Teaching Hospital launched a psychoeducation program for BD. The manual for the program is entitled “Life Goals Program” (LGP) and was designed back in 1996 by Bauer and McBride(20). LGP is a manual-based structured group psychotherapy program centered on behavioural principles from social education and self-regulation philosophies. Nevertheless, the effect of the psychoeducation in Rwanda is unexplored and psychoeducation is not part of the standard treatment.

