Inclusion criteria: A diagnosis of BD type I or II that meets DSM-V diagnostic criteria given by a trained psychiatrist and no episode in the preceding 4 weeks. Age ≥ 18 years.

Exclusion criteria: Exclusion criteria will be applied to obtain a sample reflecting the general patient population. The exclusion criteria include: Previous participation in any structured psychological intervention, such as psychoeducation or cognitive remediation, mental retardation, insufficient understanding of Kinyarwanda or deafness, alcohol or drug-dependence.

Intervention groups:

The RCT: Outpatients from the two-referral hospitals in Rwanda will be invited to participate and be allocated to intervention group or control group.

Intervention-arm: Manual-structured group psychoeducation. LGP is organized in two phases. Phase 1 of the LGP psychoeducation is mandatory and entails 8 sessions of 90 minutes over the course of 8 weeks (at one session per week) and has shown effect in western countries(21–23). Phase 2 will be offered after study completion. All groups will have 6-8 participants and two health professionals to conduct the sessions; a psychiatric nurse and either a psychologist or a psychiatric resident. Patients will be offered to invite their relatives for 2-3 psychoeducation-days for relatives.

Control group: Participants in the control group will be assigned to a waiting list and receive group-psychoeducation after the active intervention groups.

The district trial: This trial compares the impact of psychoeducation given at district level by district mental health nurses with the psychoeducation conducted at referral hospital (arm 1)

Randomization:

Study participants at the hospital level who meet the inclusion criteria and sign the informed consent form will be randomized individually into either intervention-arm or waiting list through block-randomization with a ratio of 1:1.

Patients at district level will not be randomized since we are unsure of the number of patients with BD at these levels fearing that the sample size will be too small. Instead all will be offered participation.

Outcome assessments:

All outcomes will be assessed at baseline, immediately post-intervention and at the 3rd and 6th month follow-up. The outcomes are based on the most commonly used measurements for trials on psychoeducation for individuals with BD in high and middle-income countries(18,19)

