Baseline data: The Mini-International Neuropsychiatric Interview(24) will be used to confirm psychiatric diagnosis. Demographic information regarding the participants' living circumstances, past psychiatric history and mental health service use data will also be collected from interviews and patient files.

Primary outcomes: Relapse is defined as a new mood episode of mania (scores above or equal to 20 on the Young Mania Rating Scale (YMRS)(25)), hypomania (above or equal to 12 on the YMRS), or depression (above or equal to 17 on the Hamilton Depression Scale-17(HDRS-17(26)) or mixed episode (above or equal to 20 on the YMRS and 12 on the HDRS-17).

Secondary outcomes: The Clinical Global Impression (CGI-I /CGI-S) will be used for the clinicians to assess how much the participant's condition has improved. The Medication Adherence Rating scale (MARS) will be used to assess the adherence. All participants will fill in questions about self-stigma before and after the psychoeducation.

Tertiary outcomes: A seven-item questionnaire based on The theoretical framework of acceptability(27) will be used to access the acceptability of the intervention.

The Young Mania Rating Scale and The Medication Adherence Rating scale both needs to be cultural adapted and validated using a forward–backward translation, consensus conference and cognitive interviews (approx. 15).

Sample size:

In the literature on group-psychoeducation, 13 out of 18 RCT's have reduction in general psychiatric symptom severity, incidence of relapse and hospitalization as main outcomes(18). We reviewed 18 RCT's on group psychoeducation for BD before we selected a study of Colom et al. as the base of our power calculation(18,28). The incidence of relapse in the study was (92%) (55 subjects) in the control group vs. 67% (40 subjects) in the psychoeducation group. For our study a sample size of 40 patients for each arm is required to achieve a level of 80% power with a 5% level of significance, when comparing the mean change in each intervention with the control arm via a two-sample t-test. Adjusting for a drop-out rate of 20%: $40/(1-(20/100)) = 50$ participants will be needed for each group.

Finally, for a one-year period, descriptive data on all inpatients with age > 18 years, discharged from Ndera the only inpatient psychiatric hospital, will be collected from files.

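### The wait-list rule lets controls start psychoeducation before their 3- and 6-month relapse assessments, and no readable text prevents it

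*Protocol*

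**What the plan says.** Under Intervention groups, the control arm of the RCT is described in one sentence: "Participants in the control group will be assigned to a waiting list and receive group-psychoeducation after the active intervention groups". No week, month or visit is named.

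The preceding paragraph, on the intervention arm, gives the length of the active course: "Phase 1 of the LGP psychoeducation is mandatory and entails 8 sessions of 90 minutes over the course of 8 weeks". It also says of the later phase: "Phase 2 will be offered after study completion".

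Under Outcome assessments: "All outcomes will be assessed at baseline, immediately post-intervention and at the 3rd and 6th month follow-up". The primary outcome is relapse, defined by cut-offs on the mania and depression scales, so it falls under this schedule.

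The Sample size section takes its relapse rates from an earlier trial: "The incidence of relapse in the study was (92%) (55 subjects) in the control group vs. 67% (40 subjects) in the psychoeducation group". It concludes that "a sample size of 40 patients for each arm is required to achieve a level of 80% power" and raises this to 50 per group for 20% drop-out. The Project background notes that in Rwanda "psychoeducation is not part of the standard treatment".

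**The concern.** The event that releases controls from the waiting list is the end of the active groups, not the end of the controls' own follow-up. An active course takes 8 weeks and follow-up runs to month 6. A site could therefore obey the rule and begin treating controls at about week 8, ahead of both later visits.

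At those visits the trial would then compare early with delayed psychoeducation. If psychoeducation reduces relapse, treating controls lowers their relapse rate and shrinks the observed difference. Because this is a matter of trial conduct, an analysis plan could not recreate an untreated control group at months 3 and 6 once controls had been treated. It could only rely on the earlier assessment or model the crossover.

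**Working it through.** **1. What the text fixes**

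| Item | Protocol | Tied to |
|---|---|---|
| Controls' course | Intervention groups, Control group | end of the active groups |
| Active course (Phase 1) | Intervention groups, Intervention-arm | 8 weeks |
| Phase 2 | Intervention groups, Intervention-arm | end of the study |
| Relapse assessment | Outcome assessments; Primary outcomes | post-intervention, months 3 and 6 |

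The control rule has three readings: after an 8-week active course, after all active groups have run, or after their follow-up. Only the third protects both later visits. The protocol does tie a treatment to study completion, but only Phase 2.

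**2. The plan's own sample size**

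Inputs from the Sample size section: p1 = 0.92, p2 = 0.67, 80% power, 5% significance (two-sided assumed). The text names a t-test but gives no mean difference or SD. The pooled two-proportion formula reproduces its figure, with p̄ = 0.795:

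n = [1.960·√(2·0.795·0.205) + 0.842·√(0.92·0.08 + 0.67·0.33)]² / 0.25² = (1.119 + 0.457)² / 0.0625 = 39.7, so 40 per arm.

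Power at 40 per arm is 0.803. Drop-out: 40/(1 − 0.20) = 50.

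**3. Illustration of early treatment of controls**

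Assumptions, none of them in the protocol:
- 92% and 67% are cumulative relapse at the last visit T. T is week 26 if 6 months is counted from baseline, or 8 + 26 = week 34 if counted from the end of the course.
- Hazards are constant: −ln(0.08)/T = 2.526/T untreated and −ln(0.33)/T = 1.109/T treated.
- Controls take the treated hazard from week X. X = 8 is the start of a course that follows directly, with full benefit at once. X = 16 is the end of that course. X = 24 is the end of a control course run over weeks 16–24, after two 8-week waves of active groups.

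Control relapse at T = 1 − exp{−[2.526·X + 1.109·(T − X)]/T}

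Share of the difference lost = (0.92 − control relapse)/0.25

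Power = Φ{[Δ − 1.960·√(2p̄(1 − p̄)/40)] / √([pc(1 − pc) + 0.67·0.33]/40)}, where pc is control relapse, Δ = pc − 0.67 and p̄ = (pc + 0.67)/2

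Example, T = 26 and X = 16: exponent (2.526·16 + 1.109·10)/26 = 1.981; control relapse 0.862; share lost 0.058/0.25 = 23%; power 0.53.

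| T (week) | X (week) | Control relapse | Share lost | Power, 40 per arm |
|---|---|---|---|---|
| 26 | 24 | 91.1% | 4% | 76% |
| 26 | 16 | 86.2% | 23% | 53% |
| 26 | 8 | 78.7% | 53% | 21% |
| 34 | 24 | 87.9% | 17% | 61% |
| 34 | 16 | 83.1% | 36% | 38% |
| 34 | 8 | 76.4% | 63% | 15% |
| either | untreated to T | 92.0% | 0% | 80% |

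**4. Price of a longer wait**

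Start from 50 per arm, keep 92% against 67%, and let drop-out exceed the planned 20%:

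| Drop-out | Analysed, control / treated | Power |
|---|---|---|
| 30% in controls only | 35 / 40 | 77% |
| 40% in controls only | 30 / 40 | 72% |
| 30% in both arms | 35 / 35 | 75% |
| 40% in both arms | 30 / 30 | 68% |

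**The case against.** The strongest reply is that this is an ambiguity, and that the document's logic favours the harmless reading. The patients are called a control group on a waiting list, all outcomes run to month 6, Phase 2 is held back until the study is over, and people with earlier psychoeducation are excluded. Figure 1 and the shading of Table 2, neither of which could be read, may show when the wait-list groups run. All of this stands as evidence of likely intent. None of it is a rule that a site must follow.

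A reader might infer that controls will be treated before month 3 or month 6. The protocol does not say so. A reader might also infer that the primary comparison as a whole would be lost. That too goes beyond the text: the readable protocol names no primary time point, and the assessment immediately after the intervention is essentially untouched on every reading. An analysis plan could rely on it.

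The objection to the numbers also has force. The rule speaks of groups in the plural, and 50 patients in groups of 6–8 make 7 or 8 groups. A start for all controls at week 8 needs those groups to run in parallel, or the rule to refer only to a matched group. With two waves the loss is much milder, which is why the week-24 rows are shown. The model is also uneven: the treated arm benefits from week 0, while in the week-16 and week-24 rows controls benefit only once their course ends. A consistent lag would raise the loss in those rows. The table shows a range and predicts nothing.

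**Conclusion.** The concern holds as a badly fixed rule of conduct. As written, it permits controls to be treated before or during the 3- and 6-month visits, and no readable sentence rules this out. If that occurred and the treatment works, the relapse comparisons at those visits would be biased toward no effect, and the untreated comparison there could not be recovered.

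The size is conditional on the assumptions listed in the working, above all constant hazards and 92% against 67% reached at the last visit. Within them, power at 40 per arm lies between about 15% and 76%, against 80% with untreated controls. The lowest figures need the earliest start and full benefit from the first session. If the harmless reading is what the sponsor intends, nothing is lost.

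It is worth correcting before enrolment because the remedy is small and the error, if made, cannot be undone. Confidence is medium, since the figure and timetable could not be checked.

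**What to change.** Add to the Control group paragraph: control participants start group psychoeducation only after completing their own 6-month assessment.

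This is a cheap improvement. It is one sentence, it adds no visits because controls are already followed to month 6, and it leaves the 40 and 50 per arm unchanged. It delays a course that is not standard treatment in Rwanda.

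The downside is that controls wait about 26 to 34 weeks from the start, which may raise drop-out above the planned 20% and is a point for the ethics committee to weigh. At 30–40% drop-out in controls or in both arms, power would be about 68–77%. That is above the early-start scenarios but overlaps the mildest crossover ones (61% and 76%), so the longer wait is not cheaper in every case. The gain that remains in all cases is a later comparison against controls who have not had the intervention.

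### The randomisation rule for two referral hospitals names no stratification by hospital; one list per hospital would remove avoidable chance imbalance at almost no cost

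*Protocol*

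**What the plan says.** Under Intervention groups, the protocol describes the RCT population: "Outpatients from the two-referral hospitals in Rwanda will be invited to participate and be allocated to intervention group or control group". Under Randomization, eligible and consenting hospital-level participants are allocated individually to the intervention or the waiting list "through block-randomization with a ratio of 1:1". That is the whole allocation rule for the RCT. It names no stratification factor, and it does not say whether one list serves both hospitals or each has its own.

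The Project background shows that the two hospitals are not alike:
- "only Ndera Hospital provides inpatient care".
- Annual outpatient visits with a bipolar diagnosis in the 2017 report were 1710 at Ndera and 700 at the Kigali teaching hospital.
- The Kigali outpatient clinic has run the Life Goals Program since September 2014. No such programme is described for Ndera.

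On delivery, the protocol says "All groups will have 6-8 participants and two health professionals to conduct the sessions". It does not say at which hospital a group meets.

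**The concern.** Blocking balances the arms in total. It balances them within each hospital only if each hospital has its own list. With one list, the share of Ndera patients in each arm is left to chance.

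The documents give some reason to expect hospital to matter. The services differ. Previous structured psychoeducation is an exclusion criterion, so the Kigali clinic's own programme may filter its eligible patients. Its staff may also know the manual better. None of this proves that relapse risk differs between the hospitals, but it makes hospital a natural stratification factor.

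At stake is some precision in a small trial, and the awkwardness of explaining a visible hospital imbalance afterwards. The timing also matters: an analysis plan can add adjustment for hospital later, but it cannot change the allocation list once patients have been randomised.

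**Working it through.** **Inputs**
- Two hospitals, 1:1 blocks (Intervention groups, Randomization).
- 50 patients per arm, so N = 100 (Sample size). The Feasibility section instead requires 150 from the referral hospitals, so both totals are tried.
- Hospital mix q = 1710/(1710 + 700) = 0.71. This is an assumption, because the counts are visits and not patients or expected enrolment.
- Block sizes of 4 and 8, both assumed.
- Relapse gap between hospitals of 10–20 points, assumed; the documents give no figure.

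**The plan's own figure.** "The incidence of relapse in the study was (92%) (55 subjects) in the control group vs. 67% (40 subjects) in the psychoeducation group". The two-proportion formula with 92% and 67%, two-sided 5%, 80% power, pooled variance and no continuity correction gives 40 per arm (power 80.3%). This matches "a sample size of 40 patients for each arm is required to achieve a level of 80% power with a 5% level of significance". With 20% dropout, 40/0.8 = 50. Stratification by hospital enters none of these steps.

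**Imbalance with one list.** The SD of the between-arm difference in hospital share is √(4q(1−q)/N).
- N = 100: √(4 × 0.71 × 0.29/100) = 9.1 points, so the 95% range is ±1.96 × 9.1 = about ±18 points. With a 50:50 mix it is about ±20.
- N = 150: SD 7.4 points, 95% range about ±15. With a 50:50 mix it is ±16.

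Simulated allocations at the 71:29 mix:

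| N | Lists | Difference of 10 points or more | Difference of 20 points or more |
|---|---|---|---|
| 100 | one | 29–32% | 3–4% |
| 100 | one per hospital | about 0 | about 0 |
| 150 | one | about 18–19% | about 1% |
| 150 | one per hospital | about 0 | about 0 |

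With separate lists in blocks of 4 at N = 100, the SD falls from 9.1 to about 1.4 points.

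**Effect on the treatment contrast.** Shift = imbalance × relapse gap between hospitals.
- 18 points × 0.10 = 1.8 points.
- 18 points × 0.20 = 3.6 points.

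The planned difference is 92 − 67 = 25 points, so even an imbalance at the 95% limit moves the estimate by 1.8/25 = 7% to 3.6/25 = 14% of it.

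**Effect on precision.** At 50 per arm, the standard error of the difference is √[(0.92 × 0.08 + 0.67 × 0.33)/50] = 7.7 points. The part due to hospital imbalance has SD 9.1 × 0.10 = 0.9 to 9.1 × 0.20 = 1.8 points. Its share of the variance is (0.9/7.7)² = about 1% to (1.8/7.7)² = about 5%.

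**Effect on type I error.** In 8,000 simulated trials per setting (N = 100, blocks of 4, hospital gaps of 0, 10 and 20 points), the unadjusted test rejected a true null in 5.3–5.7% of trials with one list and 4.3–5.4% with separate lists. The mean imbalance was zero in both cases.

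**The case against.** The strongest reply is that the protocol is silent and has not made a wrong choice. A reader might infer that the blocks are unstratified, but block randomisation at 1:1 fits a list per hospital just as well. That stands: the imbalance figures apply only if one list is used. It does not remove the point, because the allocation scheme has to be settled before the first patient is randomised and this is the only text that sets it.

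Second, adjustment for hospital may already be planned in an analysis plan that is not shown, and it would recover much of the lost precision. That also stands.

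Some stronger readings are tempting, and the documents do not support them:
- **Bias.** Chance imbalance averages zero over repetitions and is part of the random error that the test already allows for.
- **A large shift.** A 30-point relapse gap between hospitals with a 20-point imbalance would give 0.30 × 20 = 6 points. That gap cannot occur in the control arm at 92% relapse and a 71:29 mix. If the larger hospital were at 100%, the smaller would be at (0.92 − 0.71)/0.29 = 72.4%, a gap of 27.6 points. If the smaller were at 100%, the larger would be at (0.92 − 0.29)/0.71 = 88.7%, a gap of 11.3 points.
- **Predictable allocations.** The protocol gives no block size and does not say that block size is fixed or known to recruiters. Leaving it out of the protocol helps concealment.
- **Hospital-specific groups and leaders.** This is plausible for outpatients attending weekly sessions, but the protocol gives only group size and staff type.

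**Conclusion.** The point holds as a low-severity improvement. The protocol names no stratification by hospital for a two-hospital trial. Under a single list, a difference in hospital share of 10 points or more would arise in about 30% of trials at N = 100, or just under one in five at N = 150.

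The consequence is modest. An imbalance at the 95% limit shifts the contrast by about 2–4 points against a planned 25, and roughly 1–5% of the variance could be removed. Neither the validity of the test nor the sample size is in question.

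The size rests on the 71:29 mix taken from visit counts, on the assumed 10–20 point relapse gap, and on one list being used. The upper part of that gap is possible at 92% control relapse only if the larger hospital has the higher risk. If the hospitals do not differ in relapse risk, nothing is lost beyond a cosmetic imbalance.

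**What to change.** In the Randomization section, state that participants are randomised individually 1:1 by block randomisation stratified by referral hospital, using a separate permuted-block list for each hospital. State also that hospital will be a factor in the primary analysis, so that the analysis reflects the design.

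The cost is preparing two lists instead of one, before randomisation starts. The sample size stays at 40 evaluable and 50 randomised per arm. If separate lists are already intended, one added sentence settles the matter.

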To ensure general capacity building extending further than our research team, we collaborate with a local partner institution in Rwanda – University of Rwanda. Furthermore, this research will be a ‘twin model’ PhD project(29) involving two PhD-students: [name] - a Rwandese psychiatrist and [name] – a Danish doctor. The twin model is based on the principles of local capacity building to ensure high scientific standards and participation by local stakeholders and prevents extractive research and scientific colonialism(29,30). This is in line with UN’s sustainable development agenda, goal 17 on partnerships (31). The project will bring together three academic institutions in a partnership: Aarhus University (AU), University of Rwanda (UR) and Copenhagen University (Competence Centre for Transcultural Psychiatry).

Segregation of duties

The different tasks and responsibilities have been divided between the two PhD-students. [name] will mainly focus on psychoeducation at the district level and the qualitative part of the study (objective 3-4-5). [name] will be

responsible for the RCT and the data collection at the referral hospitals (objective 1-2). Figure 2 illustrates “The Twin PhD model” including the shared tasks and the division of responsibilities.

Figure 2: Twin-PhD-model and the segregation of duties

Feasibility

The intervention chosen – The Life Goal Programme (LGP) – is already adapted and used in a Rwandan setting. Moreover, statistics from the 2017 annual report from the two referral hospitals show that the annual numbers of outpatient visits with a diagnosis of BD were 1710 and 700 respectively, making it highly possible to include the required 150 participants from the referral hospitals. The research team is an interdisciplinary team comprised of professionals within the field of public health, transcultural psychiatry and psychology. The Rwandan PhD applicant holds professional experience in treating mental health patients in Rwanda as a trained psychiatrist; while the Danish PhD applicant has experience from DANIDA-related partnership projects in Rwanda.

Research plan and timetable

Our planned activities for the three-year project, starting in November of 2019, are presented in Table 2. We aim to initiate data-collection in the Summer of 2020.

Table 2. Activities of the three-year project.

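### The sample-size section credits 40 per arm to a t-test on mean change, although the outcome and inputs are relapse proportions; Feasibility's 150 referral-hospital patients conflicts with 2 x 50 = 100

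*Protocol*

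**What the plan says.** All references are to the protocol.

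- **Outcome assessments, primary outcome:** "Primary outcomes: Relapse is defined as a new mood episode of mania", hypomania, depression or a mixed episode, each set by cut-offs on the mania and depression scales. Each patient has either relapsed or not.
- **Sample size, inputs:** one earlier trial of group psychoeducation is named as the base of the power calculation. "The incidence of relapse in the study was (92%) (55 subjects) in the control group vs. 67% (40 subjects) in the psychoeducation group".
- **Sample size, test:** 40 patients per arm are said to give 80% power at the 5% level "when comparing the mean change in each intervention with the control arm via a two-sample t-test". After a 20% drop-out allowance, 50 "participants will be needed for each group".
- **Randomization:** referral-hospital patients are "randomized individually into either intervention-arm or waiting list through block-randomization with a ratio of 1:1". By contrast, "Patients at district level will not be randomized since we are unsure of the number of patients with BD at these levels"; all of them are offered participation. Under Intervention groups, the district trial is compared with the psychoeducation arm at the referral hospitals, not with the waiting list.
- **Feasibility:** annual outpatient visits at the two referral hospitals (1710 and 700) are cited as "making it highly possible to include the required 150 participants from the referral hospitals".

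**The concern.** Three statements do not fit the design described around them.

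1. A t-test on mean change needs a mean difference and a standard deviation, and neither is given. The inputs are two proportions. Patients enter with no episode in the preceding 4 weeks, so relapse is a new event with no baseline value from which to take a change. A mean change in a mania or depression score would be a different outcome.
2. Comparing each intervention with control implies at least two interventions against one control. The randomised trial has one intervention arm and one waiting list.
3. The number required from the referral hospitals is given in Feasibility as 150, but the per-group figure implies 100.

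The t-test is the only statistical test the protocol names, and it carries the power claim. Left as it is, it allows either the proportion relapsed or a mean score change to be presented later as the powered comparison. An ethics committee or site also cannot tell whether the referral-hospital target is 100 or 150.

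**Working it through.** **Inputs** (Sample size section): p1 = 0.92 (control), p2 = 0.67 (psychoeducation), significance level 5%, power 80%, drop-out 20%. Sidedness is not stated; two-sided is assumed. Hence z(0.975) = 1.960 and z(0.80) = 0.842.

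**Step 1: reproduce the 40 as a comparison of proportions** (pooled variance under the null, no continuity correction).

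n = [1.960 x sqrt(2 p(1-p)) + 0.842 x sqrt(p1(1-p1) + p2(1-p2))]^2 / (p1-p2)^2

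- p = (0.92 + 0.67)/2 = 0.795, so 2 x 0.795 x 0.205 = 0.326, square root 0.571
- 0.92 x 0.08 + 0.67 x 0.33 = 0.0736 + 0.2211 = 0.2947, square root 0.543
- n = (1.119 + 0.457)^2 / 0.25^2 = 2.483/0.0625 = 39.7, so **40 per arm**; power at 40 is 80.3%

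The stated figure is reproduced from the relapse rates alone.

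**Step 2: how far this depends on the formula.**

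| Method, two-sided 5%, 80% power, 92% vs 67% | n per arm |
|---|---|
| Pooled, uncorrected | 40 (39.7) |
| Unpooled variance | 38 (37.0) |
| Arcsine | 38 |
| t-test applied to the 0/1 relapse variable | 38 |
| Continuity-corrected | 48 |

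Using the printed counts as 55/60 and 40/60 (the 60 is inferred from the percentages), the pooled formula gives 40.2, so 41 per arm, and power at 40 is 79.8%. A one-sided pooled calculation with 92% vs 67% would give 32.

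**Step 3: what the t-test as described would need.** With 40 per arm, a two-sided 5% t-test has 80% power for a standardised difference of about 0.63. The protocol states no such difference, so the calculation cannot be reproduced as worded.

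**Step 4: totals.**

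- Drop-out: 40/(1 - 0.20) = 50 per group, as stated
- Referral-hospital groups: intervention and waiting list, so 2 x 50 = **100**
- Feasibility: **150**, which equals 3 x 50
- Difference: 150 - 100 = 50, exactly one further group, but only two groups are recruited at the referral hospitals

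**The case against.** The strongest reply is that nothing numerical is wrong in the Sample size section: 40 is reproducible, 50 follows from it, and a reader can recover the intent because only relapse rates are supplied. That is right about the number, and it makes this an error of description. It does not excuse a sentence that ties the power claim to a different kind of outcome.

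A second reply is that the authors may have run a t-test routine on the 0/1 relapse variable, which gives 38, close to 40. That origin cannot be excluded. Even so, it would be a comparison of proportions, not of mean change.

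Third, 40 is not robust to every choice of test: the continuity-corrected size is 48, and Fisher's exact test has about 75% power with 40 per arm. This stands, and is a reason to name the formula when the sentence is rewritten. It does not rescue the t-test wording.

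Fourth, the phrase about each intervention may be loose drafting. The randomisation text is clear, so this is the least consequential of the three points.

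Finally, 150 may include a district group of 50, and Figure 1, which might show group sizes, is not available. But the Feasibility sentence ties the 150 to the referral hospitals and supports it with their own visit counts, and the text sets no district target. It is also true that if 150 can be recruited so can 100, so feasibility itself is not threatened. The contradiction over the required number remains.

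**Conclusion.** The concern holds. The described test and comparison do not match the binary primary outcome, the relapse-rate inputs or the two-arm randomisation. The per-arm size is sound for relapse under the uncorrected pooled two-proportion test (40 per arm, power 80.3%), assuming a two-sided 5% level and the rounded rates of 92% and 67%. With the inferred counts the power is 79.8%, which is immaterial. Separately, the referral-hospital requirement is inconsistent by 50 patients: 100 by the protocol's own arithmetic against 150 in Feasibility. That the extra 50 represents the district group is plausible but is nowhere stated.

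**What to change.** In Sample size, restate the calculation, and the primary comparison it supports, as a two-sided 5% comparison of the proportion relapsed between psychoeducation and waiting list: 92% versus 67%, uncorrected two-proportion test, 80% power, 40 evaluable and 50 enrolled per arm, 100 in total. Remove the references to mean change, to each intervention and to a t-test.

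In Feasibility, reconcile 150 with the 2 x 50 = 100 of the randomised trial. If the 150 was meant to include district patients, say so, and give their intended number separately, since they are neither randomised nor recruited at the referral hospitals.

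The cost is protocol wording only. The per-arm size stays at 40 evaluable and 50 enrolled.
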